4.1.4.1. Investigational Agent Ordering

Nirogacestat will be requested from the Stanford Investigational Pharmacy.

Nirogacestat will be delivered to and managed by the Stanford Investigational Pharmacy.

4.2. Other Procedures: Cryoablation

Cryoablation of the tumor will occur between investigational agent treatment Cycles 3 and 4, and will be performed according to standard procedures. The cryotherapy device will be an FDA-approved cryoablation system used according to its approved labeling within the Stanford University Medical Center.

Prior to the cryoablation procedure, the interventional radiologist will review cross-sectional imaging studies to formulate a treatment plan, including identifying the target lesion appropriate for treatment, the number and type of cryoablation probes needed, and the optimal percutaneous access approach. Subjects will be limited to one cryoablation treatment session at time of intervention for desmoid tumors that can be at least 50% treated with cryoablation but are < 75% cryoablutable; the cryoablation will be subtotal. For lesions that are in close proximity to freeze-sensitive tissues, such as bowel or skin, the cryoablation treatment will be performed with a safe distance (≥ 5 mm) between the edge of the tissue to be frozen (the "iceball") and the freeze-sensitive tissue.

The cryoablation procedure will be performed with general anesthesia in an MR procedure room. Limited MRI will be obtained, and the desired access site(s) will be marked on the subject's skin. After sterile preparation of the treatment field and application of local anesthesia, cryoablation probes will be sequentially placed percutaneously into the target lesion using MRI and/or ultrasound guidance. After all cryoablation probes are positioned appropriately, cryoablation will be performed with 1 or more freeze-thaw cycles. Iceball growth will be monitored by MRI. After active thawing, the probes will then be removed and sterile dressings applied. Immediate post-treatment MRI without and with contrast will be obtained.

Cryoablation of the tumor will be performed using standard technique. In brief, a total of 15-30 minutes of freezing time will be administered to the tumor in two or three freeze cycles, separated by 10-30 minutes of active and/or passive thawing using the Visual-ICE Cryoablation System. Care will be taken to avoid off-target ablation of sensitive structures such as bowel and

skin. The procedures will be performed under general anesthesia. The risks of ablation include but are not limited to ecchymosis, edema/swelling, fever, hemorrhage, infection, delayed/non-healing wound, pneumothorax, probe site paresthesia, skin burn, and injury to off-target structures. With any procedure there is a small risk of death. After ablation, the subject can expect discharge to home within 23 hours in most circumstances.

4.2.1. Regulatory Status of Cryoablation

The Visual-ICE Cryoablation System, which will be used to perform cryoablation for this study, has FDA 510(k) clearance.

Cryoablation is recognized by the National Comprehensive Cancer Network (NCCN) as a viable procedure for desmoid tumor.

Intended use:

The Visual-ICE Cryoablation System is intended for cryoablative destruction of tissue during surgical procedures. The Visual-ICE System is indicated for use as a cryosurgical tool in the fields of general surgery, dermatology, neurology (including cryoanalgesia), thoracic surgery, ENT, gynecology, oncology, proctology, and urology. The system is designed to destroy tissue by the application of extreme cold temperatures, including prostate and kidney tissue, liver metastases, tumors, skin lesions, and warts.

The Visual-ICE Cryoablation System has the following specific indications:

- Urology (ablation of prostate tissue in cases of prostate cancer and Benign Prostate Hyperplasia "BPH")
- Oncology (ablation of cancerous or malignant tissue and benign tumors, and palliative intervention)
- Dermatology (ablation or freezing of skin cancers and other cutaneous disorders. Destruction of warts or lesions, angiomas, sebaceous hyperplasia, basal cell tumors of the eyelid or canthus area, ulcerated basal cell tumors, dermatofibromas small hemangiomas, mucocele cysts, multiple warts, plantar warts, actinic and seborrheic keratoses, cavernous hemangiomas, perianal condylomata, and palliation of tumors of the skin.)
- Gynecology (ablation of malignant neoplasia or benign dysplasia of the female genitalia)
- General surgery (palliation of tumors of the rectum, hemorrhoids, anal fissures, pilonidal cysts, and recurrent cancerous lesions, ablation of breast fibroadenoma)
- ENT (Palliation of tumors of the oral cavity and ablation of leukoplakia of the mouth)
- Thoracic surgery (ablation of arrhythmic cardiac tissue cancerous lesions)
- Proctology (ablation of benign or malignant growths of the anus or rectum, and hemorrhoids)

5. TREATMENT PLAN

5.1. Treatment Assignment

This is an open-label, phase 2 single center study to evaluate the efficacy and safety of cryotherapy and nirogacestat in desmoid tumors.

The interventional model is non-randomized single group.

One interventional arm.

After the subject is determined to be completely eligible to participate in the study, the OnCore sequence number, a unique subject identifier, will be sequentially assigned.

5.2. Treatment Dose

- Nirogacestat 150 mg by mouth twice daily continuously for Cycles 1 through 3.
- Cryoablation procedure (single session) of one tumor mass between Cycles 3 and 4 of nirogacestat treatment. Nirogacestat will be held on the day of cryoablation.
- Continued systemic therapy with nirogacestat for Cycles 4 through 26. Treatment with nirogacestat may continue via this study for up to 24 months (26 cycles of treatment), unless there is progression of disease, intolerance, subject withdraws their consent, start of a new anticancer therapy (as defined in Section 5.7.2), or until one of the criteria in Section 3.7 (Subject Study Completion or Termination) occurs.
- After 24 months of treatment, if clinically indicated, subjects may transition to commercial nirogacestat supply, once subjects have completed the End of Treatment (EOT) visit and are off study.

5.3. Treatment Schedule

1 cycle of treatment is 28 days.

Reported adverse events and potential risks are described in Sections 1.3 and 7.3.

Dose modifications are described in Section 5.6.

Systemic therapy with nirogacestat will be given continuously. A single session of cryoablation will be done between Cycles 3 and 4. **Note: Imaging (staging scan) should be done prior to cryoablation procedure.** Nirogacestat will be held on the day of cryoablation. Continued systemic therapy with nirogacestat for Cycles 4 through 26. Treatment with nirogacestat may continue via this study for up to 24 months (26 cycles of treatment), unless there is progression of disease, intolerance, subject withdraws their consent, start of a new anticancer therapy (as defined in Section 5.7.2), or until one of the criteria in Section 3.7 (Subject Study Completion or Termination) occurs.

The use of cryoablation for desmoid tumor is considered standard of care. However, for the purposes of this study, the use of nirogacestat in addition to regular medical care cryoablation therapy is considered investigational.

5.4. Treatment Duration

After completion of 3 cycles of treatment with nirogacestat followed by 1 session of cryoablation between Cycles 3 and 4, nirogacestat may continue for Cycles 4 through 26. Treatment with nirogacestat may continue via this study for up to 24 months (26 cycles of treatment), unless there is progression of disease, intolerance, subject withdraws their consent, start of a new anticancer therapy (as defined in Section 5.7.2), or until one of the criteria in Section 3.7 (Subject Study Completion or Termination) occurs.

After 24 months of treatment, if clinically indicated, a subject may transition to commercial nirogacestat supply, once the subject has completed the End of Treatment (EOT) visit and is off study.

5.5. Subject Medication Diary

Subjects will be provided with a nirogacestat study medication diary. They will be instructed on how to take the study medication and how to fill in their study medication diary. When they return to clinic at each visit, unused study medication and study medication diary will be collected and reviewed by study staff.

Information captured in the diary:

- Subject ID
- Site
- Cycle number
- Assigned nirogacestat dose
- Was the dose changed by the study doctor during the cycle?
- Exact date and time when each dose was taken
- Dose taken (number of tablets taken with each dose)
- Comments (reason for any missed doses, side effects, anything else participant wants to report, etc.)
- Participant signature and date

5.6. Dose Modifications

Adverse event documentation and reporting is described in Section 7.

Dose Modification

Every effort should be made to administer treatment with nirogacestat at 150 mg BID. However, dosing should be interrupted and/or dose reduced for the adverse events (AEs) described in Table 4. For patient safety, treatment may also be modified or held to manage any AE(s), at the PIs discretion.

If a subject experiences an AE as described in Table 4, hold treatment until the AE is resolved to \leq Grade 1 or baseline.

- If the AE is resolved within 14-21 days, then treatment should be restarted at the reduced dose as described in Table 4.
- If the AE does not resolve to \leq Grade 1 or baseline after holding treatment for 22 days, decision to resume treatment should be taken very carefully by the treating physician.

Should the same \geq Grade 3 AE recur at the reduced dose, and the AE is considered related to the treatment, treatment should be permanently discontinued.

Table 4. Dose Modifications

Toxicity (NCI CTCAE)	Intervention
Gastrointestinal Toxicities	
Grade \geq 3 diarrhea persisting for \geq 3 days despite maximal medical therapy ¹	Decrease dose to 100 mg BID and/or hold nirogacestat until Grade 1 or baseline.
Grade \geq 3 nausea persisting for \geq 3 days despite maximal medical therapy	Decrease dose to 100 mg BID
Grade \geq 3 vomiting persisting for \geq 3 days despite maximal medical therapy	Decrease dose to 100 mg BID
Reproductive System Toxicities	
Grade \geq 2 premature menopause / ovarian dysfunction ^{1,2}	Decrease dose to 100 mg BID
Other Toxicities	
Grade \geq 3 skin toxicity ¹	Decrease dose to 100 mg BID
Grade \geq 3 hypophosphatemia persisting for \geq 7 days despite maximal replacement therapy and in the absence of symptoms	Decrease dose to 100 mg BID
Any clinically significant Grade \geq 3 non-hematological toxicities	Decrease dose to 100 mg BID
Grade \geq 3 hematological toxicities	Decrease dose to 100 mg BID
Anaphylaxis	Permanently discontinue
Grade \geq 3 allergic reaction	Permanently discontinue
Hepatic toxicities	See below

1 Please see below for recommendations regarding AE management

2 A dose reduction is not required for events of premature menopause / ovarian dysfunction but may be considered for symptomatic participants based on the individual benefit / risk profile. A dose interruption is not required prior to a dose reduction for reproductive system toxicities.

Select Adverse Event Management Recommendations

Diarrhea:

Subjects experiencing diarrhea considered related to nirogacestat should be treated with loperamide. The recommended initial dose is 4 mg followed by 2 mg after each unformed stool

until the diarrhea is controlled, after which the dosage should be reduced to meet individual requirements. Loperamide should be dosed according to the treating physician's medical discretion. Subjects should also receive appropriate fluid and electrolyte replacement as needed.

If diarrhea is Grade \geq 3 diarrhea and persists \geq 3 days despite maximal medical therapy, decrease nirogacestat dose to 100 mg BID and/or hold nirogacestat until the diarrhea is resolved to \leq Grade 1 or baseline.

- If the dose is held and diarrhea resolves within 14 days, then nirogacestat may be restarted at a dose of 100 mg twice daily.
- If the AE does not resolve to \leq Grade 1 or baseline after holding study treatment for 22 days, nirogacestat may be resumed at a reduced dose of 100 mg twice daily only after careful consideration by the treating physician.

Skin Toxicity / Rash:

Non-acneiform rashes / skin eruptions:

Pruritic eruptions/skin rash and other non-acneiform rash should be treated with a moisturizer such as Cerave or Eucerin or another equivalent product. If symptomatic, a low-potency topical steroid such as betamethasone valerate lotion (0.05%), desonide cream (0.05%), fluocinolone acetonide solution (0.01%), dexamethasone sodium phosphate cream (0.1%), hydrocortisone acetate cream (1%), methylprednisolone acetate cream (0.25%) or equivalent may also be used.

Acneiform rash:

Topical clindamycin (0.1%) gel or lotion applied BID, rather than steroids, is the most helpful for pustular rash. In severe cases, semisynthetic oral tetracyclines such as doxycycline or minocycline may also be useful with appropriate precautions in women of childbearing potential.

Follicular cysts:

Follicular cysts can be associated with disruptions of the gamma secretase and notch signaling pathway which help maintain pilosebaceous gland function. This adverse reaction was observed in a phase 2 study of nirogacestat in desmoid tumor subjects conducted by the National Cancer Institute (O'Sullivan, 2018).⁵ If this event is suspected, it is recommended that a dermatology consultation is obtained for appropriate management recommendations.

Premature menopause / Ovarian dysfunction (OD):

Events of early menopause, such as amenorrhea and hot flushes have been commonly reported in women receiving nirogacestat. It is unknown if these symptoms are reversible after stopping nirogacestat. The effects on long-term fertility are also unknown at this moment.

In the Phase 3 DeFi Trial evaluating nirogacestat in adult patients with progressing desmoid tumors, ovarian dysfunction, which was defined by investigator-reported events of amenorrhea, premature menopause, menopause, and ovarian failure, was observed in 75% (27/36) of women of childbearing potential receiving nirogacestat. These events resolved in 74% (20/27)

of the affected participants, including 64% (9/14) of such participants who remained on nirogacestat treatment and 100% (11/11) of those participants who discontinued treatment for any reason.²⁷

Consultation with either a reproductive endocrinologist or OB/GYN experienced with ovarian dysfunction may be considered for further information regarding treatment options for OD. For example, symptoms of OD may be treated with:

- Low dose selective serotonin reuptake inhibitors
- Clonidine
- Hormone replacement therapy (HRT): Given the potential impact of hormone fluctuations on desmoid tumors, HRT should be considered on a case-by-case basis in subjects with desmoid tumors.

A dose reduction of nirogacestat to 100 mg twice-daily may also be considered for symptomatic study participants; however, at this time, there is no data to support whether this will result in symptom resolution.

Discontinuation of Treatment (See also Section 3.7)

It may be necessary for a subject to permanently discontinue treatment with nirogacestat.

Reasons for discontinuation of treatment may include:

- Any serious adverse event (SAE), clinically significant AE (refer to QTcF stopping criteria below), severe laboratory abnormality (refer to liver stopping chemistry stopping criteria below), any Grade ≥ 3 hypersensitivity reaction, anaphylaxis, intercurrent illness, or other medical conditions which indicate that continued treatment is not in the best interest of the subject;
- Pregnancy
- Termination of the treatment protocol by the Institutional Review Board (IRB) / Ethics Committee (EC) or the regulatory authority.

Liver Chemistry Stopping Criteria

Discontinuation of treatment for abnormal liver function should be considered when a subject meets one of the conditions outlined in Figure 1 or if it is believed that it is in the best interest of the subject.

- See also Appendix G: Liver Safety: Suggested Actions and Follow-up Assessments.

[figure not shown]

Figure 1. Liver Chemistry Stopping Criteria and Increased Monitoring Algorithm. Abbreviations: ALT = alanine transaminase; INR = international normalized ratio; SAE = serious adverse event; ULN = upper limit of normal.

- **Report as an SAE if adverse event is possible Hy's Law case:**
ALT $\geq 3 \times$ ULN and bilirubin $\geq 2 \times$ ULN ($> 35\%$ direct) or INR > 1.5 , if measured.*

*INR value not applicable to participants on anticoagulants.

Abbreviations: ALT = alanine transaminase; INR = international normalized ratio; SAE = serious adverse event; ULN = upper limit of normal.

QTcF Stopping Criteria

If a clinically significant finding is identified (including, but not limited to changes from baseline in QT interval corrected using Fridericia's formula [QTcF] after enrollment), the investigator or qualified designee will determine if the participant can continue in the study and if any change in participant management is needed. Any new clinically relevant finding must be reported as an AE. A participant who meets either bulleted criterion based on ECG readings will be withdrawn from study treatment:

- QTcF > 500 msec
- Change from baseline of QTcF > 60 msec

Table 5 describes discontinuation criteria for participants with underlying bundle branch block.

Table 5. Bundle Branch Block Discontinuation Criteria

Baseline QTcF with Bundle Branch Block	Discontinuation QTcF Threshold with Bundle Branch Block
< 450 msec	> 500 msec
450 to 480 msec	≥ 530 msec

Pregnancy

A female who becomes pregnant should be withdrawn from treatment with nirogacestat.

Details of all pregnancies in female participants and female partners of male participants will be collected after the start of study treatment, and pregnancies will be followed until term. See also Sections 3.8, 6.0, 7.2.4 and 7.6.

If a pregnancy is reported, the investigator must inform SpringWorks within 72 hours of learning of the pregnancy by completing Stanford SAE form and submitting to SpringWorks via email at [contact].

Abnormal pregnancy outcomes (eg, Spontaneous abortion, fetal death, stillbirth, congenital anomalies, ectopic pregnancy) are considered SAEs.

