GS inhibition may affect the intestinal tract epithelium (Barker, 2007; Kurokawa, 2020), villus lacteals (Norden, 2021), and enteric nervous system (Willem, 2016; Barrenschee, 2015), and lead to diarrhea, which could in turn lead to loss of electrolytes. In addition, Notch signaling in the nephron is responsible for the maintenance of the balance of epithelial cell type diversity and epithelial repair (Mukherjee, Fogarty, et al, 2019), and

disruption of this balance could lead to altered ability of the kidney to adapt to impaired electrolyte imbalances (Mukherjee, deRiso, et al., 2019).

Electrolyte abnormalities occurred in participants taking nirogacestat in Study NIR-DT-301. This included hypophosphatemia (42%) and hypokalemia (12%). Grade 3 events occurred in 3% and 1% of participants, respectively. Phosphate and potassium levels should be monitored regularly and supplemented as necessary. See also Section 5.6 Dose Modifications.

- **Elevated Liver Transaminases:**

Effects on hepatic function emerged as an AE of special interest for nirogacestat based on observations of mild hepatic vacuolation in nonclinical studies in rats, and transient transaminase elevations in early clinical studies with nirogacestat.

ALT or AST elevations occurred in 20% of participants who received nirogacestat in Study NIR-DT-301. Grade 3 ALT or AST elevations (> 5 times ULN) occurred in 3% of participants. The majority of ALT or AST elevations were Grade 1 (> ULN to 3 times ULN), occurred within the first month of treatment, and resolved spontaneously without dose modification. Liver function tests should be monitored regularly. See Section 5.6 Dose Modifications and Section 13.8 Appendix G Liver Safety: Suggested Actions and Follow-up Assessments.

- **Embryo-fetal Toxicity:**

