13.7. Appendix G. Liver Safety: Suggested Actions and Follow-up Assessments

Liver Chemistry Stopping Criteria	
ALT-absolute	ALT $\geq 5 \times$ ULN
ALT Increase	ALT $\geq 3 \times$ ULN persists for ≥ 4 weeks
Bilirubin^{a,b}	ALT $\geq 3 \times$ ULN and bilirubin $\geq 2 \times$ ULN ($> 35\%$ direct bilirubin)
INR^b	ALT $\geq 3 \times$ ULN and INR > 1.5 , if INR measured
Cannot Monitor	ALT $\geq 3 \times$ ULN and cannot be monitored weekly for 4 weeks
Symptomatic^c	ALT $\geq 3 \times$ ULN associated with symptoms (new or worsening) believed to be related to liver injury or hypersensitivity
Suggested Actions and Follow-up Assessments	
Actions	

 Immediately discontinue study treatment (nirogacestat) Complete the SAE eCRF form if the event meets the criteria for an SAE^b Perform liver chemistry follow-up assessments Monitor the participant until liver chemistry test abnormalities resolve, stabilize, or return to baseline Restart/rechallenge is not allowed per protocol and not granted, permanently discontinue study treatment and continue participant in the study for any protocol specified follow up assessments. 
If ALT $\geq 3 \times$ ULN AND bilirubin $\geq 2 \times$ ULN or INR > 1.5:
 
 Repeat liver chemistry tests (include ALT, AST, alkaline phosphatase, bilirubin and INR) and perform liver event follow-up assessments within 24 hours Monitor participant twice weekly until liver chemistry test abnormalities resolve, stabilize, or return to baseline A specialist or hepatology consultation is recommended 
If ALT $\geq 3 \times$ ULN AND bilirubin $< 2 \times$ ULN and INR ≤ 1.5:
 
 Repeat liver chemistry tests (include ALT, AST, alkaline phosphatase, bilirubin and INR) and perform liver chemistry follow-up assessments within 24 to 72 hrs. Monitor participants weekly until liver chemistry abnormalities resolve, stabilize, or return to baseline. 	
Follow-up Assessments	

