
 Viral hepatitis serology^d Obtain INR and recheck with each liver chemistry assessment until the transaminases values show downward trend Serum CPK and LDH Fractionate bilirubin, if total bilirubin $\geq 2 \times$ ULN Obtain complete blood count with differential to assess eosinophilia Record the appearance or worsening of clinical symptoms of liver injury, or hypersensitivity, on the AE eCRF page Record use of concomitant medications (including acetaminophen, herbal remedies, and other over-the-counter medications) on the concomitant medications eCRF page. 
ALT $\geq 3 \times$ ULN and bilirubin $\geq 2 \times$ ULN or INR > 1.5:
 
 Anti-nuclear antibody, anti-smooth muscle antibody, Type 1 anti-liver kidney microsomal antibodies, and quantitative total IgG or gamma globulins. Serum acetaminophen adduct HPLC assay (quantifies potential acetaminophen contribution to liver injury in participants with definite or likely acetaminophen use in the preceding week [James, 2009]). Liver imaging (ultrasound, magnetic resonance, or computerized tomography) and/or liver biopsy to evaluate liver disease; complete liver 	

AE = adverse event; ALT = alanine aminotransferase; AST = aspartate aminotransferase; CPK = creatine phosphokinase; eCRF = electronic case report form; HPLC = high performance liquid chromatography; IgG = immunoglobulin G; INR = international normalized ratio; LDH = lactate dehydrogenase; SAE = serious adverse event; ULN = upper limit of normal.

- a. Serum bilirubin fractionation should be performed if testing is available. If serum bilirubin fractionation is not immediately available, discontinue study treatment if $ALT \geq 3 \times ULN$ and bilirubin $\geq 2 \times ULN$. Additionally, if serum bilirubin fractionation testing is unavailable, record the absence/presence of detectable urinary bilirubin on dipstick which is indicative of direct bilirubin elevations suggesting liver injury.
- b. All events of $ALT \geq 3 \times ULN$ and bilirubin $\geq 2 \times ULN$ ($> 35\%$ direct bilirubin) or $ALT \geq 3 \times ULN$ and INR > 1.5 may indicate severe liver injury (possible 'Hy's Law') and must be reported as an SAE (excluding studies of hepatic impairment or cirrhosis). The INR stated threshold value will not apply to participants receiving anticoagulants.

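### Section 5.6 leaves stopping nirogacestat for liver toxicity to judgement, while Appendix G orders an immediate and permanent stop

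*Protocol*

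**What the plan says.** In Section 5.6, the hepatic row of Table 4 gives no action and sends the reader to the text below it. The operative sentence there, under the liver chemistry stopping criteria, is: "Discontinuation of treatment for abnormal liver function should be considered when a subject meets one of the conditions outlined in Figure 1". The sentence goes on to allow stopping when that is thought best for the subject. It is followed by "See also Appendix G: Liver Safety: Suggested Actions and Follow-up Assessments" and by Figure 1, whose caption says that it covers both stopping criteria and increased monitoring.

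Appendix G (Section 13.7) lists six stopping criteria:
- ALT at or above 5 x ULN;
- ALT at or above 3 x ULN persisting for 4 weeks or more;
- ALT at or above 3 x ULN with bilirubin at or above 2 x ULN (more than 35% direct);
- ALT at or above 3 x ULN with INR above 1.5;
- ALT at or above 3 x ULN that cannot be monitored weekly for 4 weeks;
- ALT at or above 3 x ULN with symptoms.

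The action block is headed as suggested. Its first bullet is "Immediately discontinue study treatment (nirogacestat", and a later bullet reads "Restart/rechallenge is not allowed per protocol and not granted, permanently discontinue study treatment". Footnote a, on the bilirubin criterion, is also an instruction: "If serum bilirubin fractionation is not immediately available, discontinue study treatment if" the ALT and bilirubin thresholds are met.

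**The concern.** A stopping rule should have one force. Here the body of the protocol asks the investigator to think about stopping, and the appendix tells the investigator to stop at once and never restart. Nothing in the readable text ranks the two.

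The clash matters in one situation: a subject meets a criterion and the investigator wants to carry on with nirogacestat. Section 5.6 leaves that open and Appendix G forbids it. The criteria include the pattern that Appendix G itself labels as possible Hy's Law, so the softer wording reaches the most serious liver signal in the protocol. Two people judging the same case could also disagree on whether continuing is a protocol deviation to be documented under Section 9.2.2.

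**Working it through.** **Comparing the texts.** No figure in the plan needs reproducing; the check is on wording.

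| Place | Instruction once a criterion is met | Force |
|---|---|---|
| 5.6, liver paragraph | stopping is to be considered | discretionary |
| Appendix G, title and action heading | actions are suggested | advisory label |
| Appendix G, first action bullet | stop immediately | imperative |
| Appendix G, restart bullet | no restart or rechallenge; permanent stop | prohibition |
| Appendix G, footnote a | stop, when bilirubin cannot be fractionated at once | imperative |

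The restart bullet decides how the appendix should be read. A statement that something is not allowed per protocol cannot be only a suggestion, whatever heading it sits under. On its actions, then, Appendix G is mandatory, and the liver sentence in 5.6 is not.

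Section 5.6 uses firm wording when a firm stop is meant. A subject who meets a QTcF criterion will be withdrawn from treatment, and Table 4 calls for permanent discontinuation for anaphylaxis and for Grade 3 or higher allergic reaction.

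On restart there is no conflict. The liver paragraph of 5.6 has no restart rule, so the bar in Appendix G is the only liver-specific text.

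**How often it could arise, through the absolute ALT criterion only.**

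Inputs:
- Grade 3 ALT elevation in 2 of 69 nirogacestat subjects in the phase 3 study (Tables 1 and 6).
- The Grade 3 threshold, from Section 7.3.1: "Grade 3 ALT or AST elevations (> 5 times ULN) occurred in 3% of participants". Grade 3 ALT therefore stands in for ALT at or above 5 x ULN.
- 20 evaluable and up to 23 enrolled subjects (Section 10.4.1).

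Calculation:
- p = 2/69 = 0.0290; exact (Clopper-Pearson) 95% interval 0.0035 to 0.1008.
- Expected number at similar exposure: 20 x 0.0290 = 0.58; 23 x 0.0290 = 0.67.
- At the interval limits: 20 x 0.0035 = 0.07 to 20 x 0.1008 = 2.02; 23 x 0.0035 = 0.08 to 23 x 0.1008 = 2.32.

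The protocol does not give exposure time in phase 3. If exposure here were k times as long, at constant hazard, the risk is q = 1 - (1 - p)^k. Taking k from 0.5 to 2 as an assumption:
- k = 0.5: q = 0.0146, so 0.29 of 20 or 0.34 of 23.
- k = 2: q = 0.0571, so 1.14 of 20 or 1.31 of 23.

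These count subjects who would reach the criterion. The wording decides the outcome only if the investigator then wants to continue, and the documents give no probability for that. Nor do they give rates for the other five criteria, which are not counted.

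**The case against.** The strongest reply is that the operative rule may lie in Figure 1, which is not readable in the copy reviewed. Its caption covers monitoring as well as stopping, so a softer lead-in would be sensible if some branches call only for monitoring. This stands as a reason to look at Figure 1 before editing and to leave any monitoring branch alone. It does not remove the conflict. The printed sentence in 5.6 governs how the figure is used, and it stays discretionary even if the figure says to stop.

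A second reply is that stopping satisfies both texts, and that an investigator who follows the cross-reference meets the stricter one. That is true, but the gap concerns continuing. If Appendix G were only advisory, continuing would breach nothing; the ban on rechallenge makes that reading hard to hold.

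A reader might infer that 5.6 is permissive in a second place, because its list of reasons that may lead to discontinuation includes "severe laboratory abnormality (refer to liver stopping chemistry stopping criteria below". The documents do not support this. The same list names anaphylaxis and points to the QTcF criteria, both mandatory stops elsewhere in 5.6. The list only collects reasons and does not set the force of any of them.

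A reader might also take 0.6 to 0.7 subjects as a ceiling. It is an expected value, and the interval reaches 2.3.

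**Conclusion.** The inconsistency is real and minor. Section 5.6 and Appendix G give different force to the same liver stopping rule, and the readable text does not say which governs. Through the absolute ALT criterion, about 0.6 to 0.7 of 20 to 23 subjects would be expected to reach the rule, roughly 0.1 to 2.3 across the exact interval. This assumes exposure similar to phase 3 and takes Grade 3 ALT as a proxy for the criterion.

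It would go too far to say that the protocol makes liver stopping optional throughout, or that the trial's inference is affected. Appendix G does order the stop, and alpha, power and sample size are untouched.

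**What to change.** First check Figure 1, and keep any monitoring-only branches as they are. Then:

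1. In Section 5.6, replace the liver sentence with: *Nirogacestat will be permanently discontinued, without rechallenge, when a subject meets any Liver Chemistry Stopping Criterion in Appendix G; it may also be discontinued if this is in the subject's best interest.*
2. In Appendix G, mark the discontinue and no-rechallenge bullets as required. Leave the work-up as suggested.

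The cost is one sentence and one heading, with no added tests. The downside is that the few subjects who meet a criterion lose the drug and the investigator loses discretion. If the sponsor prefers to keep discretion, Appendix G would have to be softened instead; either way the two places should agree.

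A clerical slip can be corrected in the same edit: Section 7.3.1 places Appendix G in Section 13.8, but it is Section 13.7.
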